6.5 Precautions in Handling M032

Sterile technique and Biosafety Level 2 precautions (gown, gloves, mask) will be rigorously followed while preparing the dose. The dose preparations will take place in a biosafety hood.

6.6 Precautions in Disposal of M032

All materials that have been in contact with M032 are considered infectious biohazards, and must be decontaminated or incinerated prior to disposal. Needles and syringes should be placed into a puncture-resistant, leak-proof container containing disinfectant. Instruments should be placed in disinfectant or swabbed with disinfectant soaked gauze sponges that are then discarded appropriately. Instruments should be well cleaned and autoclaved. All disposable materials that have been in contact with the vector must be incinerated or microwaved in an institutionally approved biohazard incinerator/microwave device before disposal.

7. CORRELATIVE/SPECIAL STUDIES

To address secondary objectives of the protocol, additional correlative studies will be performed on blood/serum, conjunctival secretions, saliva samples and tumor tissue samples.

Blood Samples: Blood samples (heparinized) will be taken at Baseline, on Days 0, 2, 3, 10, 28 and at Months 3, 6, 9 and 12. One ml of each sample will be submitted to the Clinical Virology Diagnostic Laboratory for HSV culture to determine the amount of virus shedding. The balance of the blood sample will be separated by density gradient centrifugation to provide plasma (serum) and peripheral blood mononuclear cells (PBML). Plasma will be tested to permit detection and quantification of HSV antibody titer pre-and post-inoculation via ELISA. Peripheral blood mononuclear leukocytes will be quantified for subsets and other leukocyte markers by FACS analysis, expression of activation signals (intracellular lymphocyte interferon-gamma levels) and lymphocyte transformation assays will also be performed to assess aspects of the T_H1 response to treatment with M032. Plasma cytokine assays will be performed to quantify changes over time from baseline. Conjunctival, blood and saliva will be assessed for HSV shedding by standard culture methods. Any positive cultures will be further

characterized for wild-type or M032 HSV by PCR. Any remnant blood will be stored for future brain tumor research.

Tissue Samples: If available, remnant brain tissue from the biopsy will be snap-frozen in liquid nitrogen and stored for future research. Should any patient with recurrent tumor after HSV treatment be determined to benefit from additional tumor resection for diagnosis or to ameliorate intractable symptoms caused by increased mass effect and intracranial edema, the tumor will be removed *en bloc* as much as possible and sectioned in 2-4mm thick slices perpendicular to the placement of the catheters. Each section will be cut into quarters and each quarter will be labeled 1, 2, 3 or 4, processed and stored for future research as follows:

Quarter 1: Snap freeze in liquid nitrogen for immediate assessment of viral replication *in vitro*.

Quarter 2: Snap freeze in liquid nitrogen for RNA and DNA extraction and the following evaluations:

- Quantitative PCR (vector replication *in-vivo*; compare number of copies to vector input)
- RT-PCR to detect HSV polymerase mRNA (vector replication *in-vivo*)
- Confirmation and quantification of M032 presence by quantitative PCR of IL-12 recombinant DNA
- Confirmation and quantification of human IL-12 production by M032 by use of RT-PCR to the internal ribosomal entry site (IRES) sequence present between the p35 and p40 subunits of IL-12 in M032

Quarter 3: Snap freeze in liquid nitrogen for subsequent tissue homogenization and the following evaluations:

- Confirmation and quantification of IL-12 production by use of a p70 ELISA kit after laser capture microdissection
- Quantification of *in situ* interferon- γ production by use of Multiplex Bead and ELISA kits

[figure not shown]
Quarter 4: Processed as routine histopathology in formalin for:

- Routine histopathology (H & E, GFAP, MIB, etc.)
- Immunohistochemistry for HSV-1, glycoprotein C (gC) when possible
- Characterization of the nature of the inflammatory infiltrate by reaction with monoclonal antibodies for CD4, CD8 and macrophage markers

Subsequent 2-4mm thick Slices if available):

- Process 2 quadrants of each slice in formalin as routine histopathology; may be used for further characterization of the inflammatory infiltrate as needed
- Snap freeze 2 quadrants of each slice in liquid nitrogen; may be used for further studies, such as laser capture microdissection, RNA and DNA extraction as needed, etc.

Schematic for Processing of Tumor Tissue

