9.3.4 Pseudoprogression

Pseudoprogression is a well-known entity in oncolytic viral therapy of glioma. Currently, the immunotherapy Response Assessment in Neuro-Oncology (iRANO) group is proposing criteria for determination of pseudoprogression in immunotherapy trials which are not yet published. [40] We will utilize the following criteria to address this phenomenon in this trial : If tumor appears to enlarge or demonstrates increased enhancement by MRI consistent with PD, patients will undergo repeat imaging and clinical assessments at 3 months to determine whether the changes demonstrate true progression or pseudoprogression. Note that the investigator may obtain an MRI prior to this 3 month interval as indicated. Should significant neurologic deterioration occur that cannot be ascribed to tumor or pseudoprogression related events such as seizures or medication changes (e.g., steroid tapers) the patient will be considered to have progressed. During the interval, the patient may be watched or treated with bevacizumab and/or dexamethasone at the discretion of the investigators. If the patient improves with bevacizumab (to be used

preferentially at a suggested dose of 10mg/kg IV, every two weeks, for three months; previous tumor progression on bevacizumab does not preclude its use herein) and/or additional steroid administration (to be used if bevacizumab is contraindicated or insufficient) and the MRI changes in lesion size/and or enhancement also improves, the patient will be determined to have not progressed but to have suffered pseudoprogression, and will continue follow-up within the trial under the previously defined schedule. Should neurologic symptoms and/or imaging changes progress despite steroid administration on follow-up imaging, the patient will be determined to have progressed and the date of progression shall be assigned to the date of the initial scan that demonstrated findings consistent with PD as defined above.

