11.1 Study Design/Endpoints

This study is an open-label, dose escalating phase 1 study of the safety of intracranial administration of

M032, a genetically engineered HSV-1 expressing IL-12. For this reason, the primary endpoints of this study is to determine the safety and tolerability of a single 12 hour stereotactic intracerebral infusion of escalating doses of M032 virus, and to determine the maximally tolerated dose (MTD) of M032. The dose escalation scheme and the definition of the MTD are found in **Section 4.2**. Because M032 is administered as a single dose (although that single dose may be delivered via different catheters), intra-patient dose escalations will not be feasible.

Demographic Analysis: Demographic and baseline characteristics will be summarized for each cohort using the statistics of number, mean, median and range for continuous variables and for discrete factors, values will be tabulated.

Safety Analysis: Descriptive statistics will be used in the reporting of adverse events. Adverse events will be tabulated and frequencies of events will be determined. All events with a toxicity of Grade 3 or above (except as discussed in section 4.2) will be tabulated by event, as well as tabulations for all events (where toxicity is defined by the CTCAE, version 4.0). Laboratory analyses (chemistries, hematology, urinalysis, serological/immunological analyses, WBC and differential) will consist of measurements of change from baseline over time by patient and overall, with plots of actual values compared to normal values for patients by dose group. Logarithmic transformations may be applied as necessary. Group means and standard errors will be calculated for the various laboratory parameters. Concurrent Illnesses will be listed and examined by univariate and multivariable analysis as possible confounders in the treatment response relationship. Concurrent medications will also be listed. Effects of previous treatments for cancer will also be examined by univariate and multivariable analysis, and any potential related side effects will be analyzed and discussed.

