11.4 Analysis of Secondary Endpoints

11.4.1 Delineation of the local and systemic immune response to M032 administration.

- Virus reactivation and shedding will be detected by PCR and culture of serial serum and saliva samples.
- Immunogenicity of M032 will be evaluated by the use of ELISA to detect HSV antibody titers.
- Each of these binomial responses will be summarized by frequencies for each cohort and overall.

11.4.2 Gather preliminary information about the potential benefit of M032 in the treatment of patients with recurrent malignant gliomas.

- The percentage of patients experiencing complete response, partial response, stable disease and progressive disease will be reported by cohort and overall based on follow-up radiographic imaging.
- Changes in clinical disease status and steroid administration will be considered when reviewing changes in tumor volumetric size.
- All changes in tumor volume will also be analyzed with consideration of any other anti-tumor cancer therapies (either prior to M032 administration or following M032 failure) and the timeframes in which they were administered.

- Quality of life response: A Karnofsky Performance Status score will be recorded pre-treatment and then measured serially post-treatment for each patient. Time to KPS <60 will be measured for each patient by the Kaplan-Meier analytical method.

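### Immune results through Month 12 are pooled as change from baseline, with no separation of samples drawn after bevacizumab, added dexamethasone or later anti-tumor therapy

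*Combined protocol and SAP*

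**What the plan says.** Section 7 sets the sampling times: "Blood samples (heparinized) will be taken at Baseline, on Days 0, 2, 3, 10, 28 and at Months 3, 6, 9 and 12". It describes the cellular assays (leukocyte subsets, intracellular interferon-gamma, lymphocyte transformation) as done "to assess aspects of the T_H1 response to treatment with M032". The next sentence covers the cytokines: "Plasma cytokine assays will be performed to quantify changes over time from baseline".

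The summary method is in Section 11.1. Laboratory results, which there include serological and immunological analyses, "will consist of measurements of change from baseline over time by patient and overall, with plots of actual values compared to normal values", and group means and standard errors are calculated. Concurrent medications are listed. The confounder models named there cover concurrent illnesses and cancer treatments given before the study.

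Section 4.3 allows bevacizumab or steroid for symptoms of edema or raised intracranial pressure. Section 9.3.4 says of suspected pseudoprogression: "During the interval, the patient may be watched or treated with bevacizumab and/or dexamethasone at the discretion of the investigators". It suggests three months of bevacizumab, and a patient then judged not to have progressed "will continue follow-up within the trial under the previously defined schedule".

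For tumor volume, Section 11.4.2 says: "All changes in tumor volume will also be analyzed with consideration of any other anti-tumor cancer therapies".

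**The concern.** Objective 1.4.1 is the local and systemic immune response to M032. A change from baseline at Month 3, 6, 9 or 12 measures that response only if nothing else given in between moves the assay. The protocol permits drugs that might, and its management text for cytokine storm (Section 5.1) says corticosteroids can reduce the cytokine response.

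The baseline is partly protected from these drugs. Sections 3.1.11 and 3.2.7 exclude a recent steroid increase, Section 3.2.15 excludes recent bevacizumab, and Section 3.2.1 excludes recent chemotherapy and immunotherapy. Follow-up samples have no matching protection, so any effect of a drug started later goes straight into the change from baseline.

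Use of these drugs is also not random. They are given for edema or apparent enlargement, and Section 4.3 links edema to how M032 is presumed to work. In a trial of 8 to 24 patients spread over several doses, one such patient can dominate a group mean.

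**Working it through.** The plan states no sample size, effect size or test for the immune assays, so there is no figure to reproduce. The check is a comparison of passages, followed by an illustration on assumed inputs.

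**1. Sampling window.** Draws after the Day 1 infusion (Section 7): Days 2, 3, 10 and 28, and Months 3, 6, 9 and 12, which is 8. Draws at Month 3 or later: 4, and 4/8 = 50%.

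**2. Overlap with permitted drugs.** Section 9.3 schedules MRI at Day 28 and Month 3, among other times. A three-month bevacizumab course begun after the Day 28 scan runs from about Month 1 to Month 1 + 3 = 4 and covers the Month 3 draw. One begun after the Month 3 scan runs to about Month 3 + 3 = 6 and reaches the Month 6 draw. Earlier draws can be affected too: Section 4.2 describes raising steroid for weakness or aphasia during the infusion.

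**3. How each kind of data treats these drugs.**

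| Data | Rule in the plan |
|---|---|
| MRI response (9.3.1) | A scan within two weeks of a steroid or bevacizumab dose change can be non-evaluable |
| Tumor volume (11.4.2) | Read with steroid use and other anti-tumor therapy in mind, including therapy after M032 has failed |
| Shedding and HSV antibody (11.4.1) | Frequencies by cohort and overall |
| Cellular and cytokine assays (7, 11.1) | Change from baseline, means and standard errors; medications listed, not linked to samples |

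The problem is handled for imaging and not carried over to the immune assays.

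**4. Illustration only.** Let f be the share of samples at a visit drawn under another drug's influence, and d that drug's shift in the assay, in units of the assay's standard deviation. The documents give neither, so f = 25% to 75% and d = 0.5 to 1.0 are assumptions. Suppose M032 has no effect and all N patients give a sample. Then:

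- shift in the pooled mean = f × d
- standard error = √(1 + f(1 − f)d²) / √N
- chance that a nominal 95% interval excludes zero: normal approximation

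| f | d | Shift (SD) | SE, N = 24 | Chance, N = 24 | SE, N = 8 | Chance, N = 8 |
|---|---|---|---|---|---|---|
| 0.25 | 0.5 | 0.125 | 0.209 | 9% | 0.362 | 6% |
| 0.50 | 1.0 | 0.50 | 0.228 | 59% | 0.395 | 24% |
| 0.75 | 1.0 | 0.75 | 0.222 | 92% | 0.385 | 50% |

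The result runs from almost no distortion to a mean that looks like a clear effect. No test is planned, so the percentages only show how a reported mean and standard error would look.

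**The case against.** The plan does not leave the reader blind. Results are shown by patient, medications are listed, and the study calendar in Section 8 records concurrent medications at every visit. No model attributes changes to M032, and the cytokine sentence makes no such attribution; the wording about response to M032 belongs to the cellular assays. Immune response is a tertiary objective in Section 1.4 (the synopsis and Section 7 call it secondary) and does not enter the dose-limiting toxicity or dose-finding rules. All of this stands, and it limits the weight of the point. It does not remedy the pooled means, and separating samples after the results are seen is a poor substitute for a stated rule.

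Several stronger readings are tempting but not supported:

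- **Most late samples reflect another drug.** A reader might assume a median time to the first such drug and use 1 − 2^(−t/median). At Month 6, assumed medians of 2, 6 and 12 months give 88%, 50% and 29%. That only restates the assumption. It also counts patients who ever started, ignores deaths, and does not describe the samples actually drawn.
- **A real response is understated where it was strongest.** Section 5.1 supports a direction for corticosteroids on cytokines, without a size. Section 9.3.4 prefers bevacizumab, and nothing in the documents says which way it moves these assays.
- **Chemotherapy effects are counted as M032 effects.** Section 4.4 continues safety evaluations after progression, but the synopsis makes outpatient visits subject to progression, Section 4.1 bars other treatment aimed at the malignancy, and the immune assays are assigned to neither the safety nor the efficacy stream. Section 11.4.2 does expect later therapy; whether immune samples follow it is unsettled.
- **Only samples before the first such drug should count.** That would remove the patients with edema or apparent progression from later visits, and a brief steroid increase on the infusion day would discard all of a patient's later samples. It replaces one bias with another.

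**Conclusion.** The concern holds as a gap in the analysis. Sections 7 and 11.1 pool immune results through Month 12 without distinguishing samples drawn after bevacizumab, a dexamethasone increase or later anti-tumor therapy, although the protocol permits the first two in that window and allows for all three when reading tumor data. Pooled late means cannot be read as the immune response to M032.

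The bevacizumab and steroid part rests directly on the text; the later-therapy part depends on whether immune sampling continues after progression, which the documents leave open. The size of the distortion is unknown: the range of 0.125 to 0.75 SD follows wholly from the assumed f and d. The primary endpoint is not affected.

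**What to change.** Add to Section 11.1, for the Section 7 immune assays:

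- Using the concurrent-medication records, flag each immune sample by whether, at the draw, the patient was receiving or had previously started bevacizumab, dexamethasone above the baseline dose, or another anti-tumor therapy. Recording current and past exposure separately keeps a short steroid increase visible as such.
- Report the all-sample summary beside a summary restricted to unflagged samples, list the flagged samples separately, and give the number of patients at each time point.
- Mark start and stop dates of these drugs on the by-patient plots.
- State that the restricted summary is itself selective, because these drugs go to patients with edema or apparent progression.

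No change to treatment or sampling is needed, and medications are already reviewed at every visit. The cost is slightly more analysis work and small numbers in the late unflagged summaries.

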8. STUDY CALENDAR

	Pre-Study (within 2 weeks prior to the administration of M032)	Day 0	Day1	Day 2	Day 3	Day 10 (± 3 days)	Day 28 (± 4 days)	Month 2 (± 12 days)	Month 3 (± 12 days)	Months 4, 5 (± 12 days)	Months 6, 9, 12 (± 12 days)	Unscheduled ²⁰
Informed consent	X ¹											
Inclusion/ Exclusion Criteria	X											
Demographics	X											
Pregnancy test-serum ⁴	X											
Medical history	X											
Concurrent meds	X	X	X	X	X	X	X	X	X	X	X	X
Complete physical exam (including wound assessment Days 1-10)	X		X	X ¹⁷	X ¹⁷	X	X		X		X	X ²¹
Vital signs	X	X	X ²	X ²	X ²	X	X		X		X	X ²¹
KPS	X				X	X	X		X		X	X ²¹
CBC w/diff, plts	X			X		X	X	X	X	X	X	X
Serum chemistry ³ , PT/INR, PTT	X			X		X	X	X	X	X	X	X
HIV serology	X											
EKG	X											
CXR (AP and lateral)	X											
Urinalysis with micro	X											
Adverse event evaluation ^{11, 12}		X	X	X	X	X	X	X	X	X	X	X
MRI ⁵	X ¹³	X			X		X		X		X	X ²¹
Neurologic exam	X	X	X ⁶	X ⁶	X ⁶	X	X		X		X	X ²¹
HSV Ab titer ⁷	X					X	X		X		X	X
HSV detection (saliva, conjunctival secretions, blood) ⁸	X			X ¹⁸	X ¹⁸ blood only	X	X	X	X	X	X	X
IL-12 detection (serum) ⁹	X			X ¹⁸	X ¹⁸	X	X		X		X	X
Blood sample for LTA, Elispot	X			X ¹⁸	X ¹⁸	X	X		X		X	X
IFN gamma assay	X			X ¹⁸	X ¹⁸	X	X		X		X	X
Blood to be stored for future immune studies	X	X ¹⁵		X ¹⁸	X ¹⁸	X	X		X		X	X
Head CT		X ¹⁰										

	Pre-Study (within 2 weeks prior to the administration of M032)	Day 0	Day 1	Day 2	Day 3	Day 10 (± 3 days)	Day 28 (± 4 days)	Month 2 (± 12 days)	Month 3 (± 12 days)	Months 4, 5 (± 12 days)	Months 6, 9, 12 (± 12 days)	Unscheduled ²⁰
Biopsy, Catheter placement		X										
Prophylactic AED	X	X	X	X	X	X	X ¹⁶					
M032 Administration			X									
Rickham/Ommaya reservoir aspiration ¹⁹	X	X	X	X	X	X	X		X		X	X ²¹

1. Will be obtained prior to study screening procedures.
2. Frequency post initiation of infusion: vital signs will be every hour for 12 hours post initiation, every 2 hours for the next 12 hours, then every 4 hours for the next 24 hours.
3. Includes sodium, potassium, chloride, bicarbonate, glucose, BUN, creatinine, calcium, phosphorus, total protein, uric acid, GGT, AST/ALT, CK, LDH, alkaline phosphatase, total bilirubin, cholesterol, triglyceride.
4. Only women of child-bearing potential. If necessary, can be repeated during the course of the study.
5. All MRI scans will be performed as prescribed by the Principal Investigator.
6. Neurological exam includes assessment of cranial nerve abnormalities, gait abnormalities (when appropriate), sensory abnormalities, muscle strength, and level of consciousness. This will be evaluated every hour for 12 hours post initiation, every 2 hours for the next 12 hours, then every 4 hours for the next 24 hours.
7. By ELISA; neutralizing antibody assays may also be performed.
8. Samples will be evaluated by PCR and culture; quantitative PCR may be performed on positive samples.
9. IL-12 detection (serum) by ELISA.
10. After catheter placement but before start of infusion; may also take place on Day 1.
11. All AEs will be assessed throughout the course of the study, but specific CRFs will only be required at the time points delineated in the above schedule.
12. All unresolved toxicities be followed regularly by the treating physician and/or research coordinator; the nurse coordinator will conduct follow-up weekly with the subject, family and/or referring physician (by phone if travel is too burdensome for the subject) until resolution of treatment-related toxicity to less than Grade 2 (or Grade 3 if that was the subject's baseline).
13. MRI's that have been obtained within 30 days of pre-study visit may be used at the discretion of the PI.
14. Sample will be stored for future brain tumor research.
15. To be obtained post-op.
16. Prophylactic AED's may be discontinued at the Day 28 visit.
17. Wound examination only.
18. Acceptable up to 2 days after
19. Should a patient have an access device (eg., Rickham or Ommaya reservoir) that accesses either the more central portion of the tumor/cyst, or the CSF space, fluid will be aspirated as possible (expected, 2-10cc) from the catheter for laboratory studies. These specimens will be obtained at either the pre op clinic visit or the day of surgery, as well as up to daily during the inpatient hospitalization (per the surgeon's discretion), and again at post op visit day 10, Day 28, and Months 3,6,9 and 12.
20. If a participant is to miss a regularly scheduled research follow-up visit, an unscheduled visit can be conducted to capture research data at an otherwise standard of care clinic visit.
21. Collected only if done during an otherwise non-research visit (i.e., unscheduled visit).

8.1 Study Procedures

Screening Phase: (within 2 weeks prior to Treatment Phase)

- Obtain informed consent before any study-related procedures are performed
- Review Inclusion/Exclusion Criteria for eligibility

- Collect the following information:
 - Demographics
 - Medical history
 - Medications currently being taken
- Obtain vital signs (pulse, blood pressure, respiratory rate, temperature, height and weight)
- Perform a complete physical examination
- Perform a neurological (nervous system) examination to include assessment of cranial nerve abnormalities, gait abnormalities (when appropriate), sensory abnormalities, muscle strength, and level of consciousness
- Complete the Karnofsky Performance Scale (KPS)

- Collect blood for the following:
 - CBC with diff and platelets
 - Serum Chemistry (sodium, potassium, chloride, bicarbonate, glucose, BUN, creatinine, calcium, phosphorus, total protein, uric acid, GGT, AST/ALT, CK, LDH, alkaline phosphatase, total bilirubin, cholesterol, triglyceride)
 - PT/INR, PTT
 - HIV Serology
 - Pregnancy test (if applicable)
 - HSV antibody titer
 - HSV detection
 - IL-12 detection
 - LTA Elispot
 - IFN gamma assay
 - Immune studies - to be stored for future research
- Collect samples of conjunctival (eye) secretions and saliva for HSV detection
- Collect urine sample for urinalysis and microscopic examination
- Obtain:
 - ECG
 - Chest x-ray
 - MRI - MRI's that have been obtained within 30 days of pre-study visit may be used at the discretion of the PI.
- All patients will be required to be placed on an anticonvulsant at the time of screening; those patients already on an anti-convulsant (anti-epileptic drug/AED) will have a second anti-convulsant added per the discretion of the investigator. This anti-convulsant will be continued for a minimum of 28 days unless the patient develops a reaction to the medication. If this develops, all attempts will be made to implement an alternative agent.
- Should a patient have an access device (eg., Rickham or Ommaya reservoir) that accesses either the more central portion of the tumor/cyst, or the CSF space, fluid will be aspirated as possible (expected, 2-10cc) from the catheter for laboratory studies. These specimens will be obtained at either the pre op clinic visit or the day of surgery, as well as up to daily during the inpatient hospitalization (per the surgeon's discretion), and again at post op visit day 10, Day 28, and Months 3,6,9 and 12

Day 0 (biopsy and catheter placement)

- Admit to the hospital for biopsy surgery and if eligible, catheter placement
- Review medications
- AE monitoring
- Obtain vital signs (pulse, blood pressure, respiratory rate, temperature and weight) prior to surgery
- Perform a neurological (nervous system) examination to include assessment of cranial nerve abnormalities, gait abnormalities (when appropriate), sensory abnormalities, muscle strength, and level of consciousness
- Obtain a stereotactic MRI to determine site for the biopsy and catheter placement
- Perform the biopsy and, if eligibility criteria are met, place and label up to 4 catheters

- Prime each catheter with 0.4 ml sterile saline solution and cap the catheters
- Admit to the Neurosurgery Intensive Care Unit for routine post-biopsy care and observation
- Obtain CT scan to ensure the catheters are in the proper position. (May be completed on Day 1 prior to drug administration)
- Collect blood for the following:
 - Immune studies - to be stored for future research – collect post-op
- Should a patient have an access device (eg., Rickham or Ommaya reservoir) that accesses either the more central portion of the tumor/cyst, or the CSF space, fluid will be aspirated as possible (expected, 2-10cc) from the catheter for laboratory studies. These specimens will be obtained at either the pre op clinic visit or the day of surgery, as well as up to daily during the inpatient hospitalization (per the surgeon's discretion), and again at post op visit day 10, Day 28, and Months 3,6,9 and 12

Day 1 (drug administration):

- If subject's condition is stable, transfer to a Clinical Research Unit inpatient bed for drug infusion and monitoring
- Review medications
- Perform a complete physical exam including wound assessment
- If not completed on Day 0, obtain a CT scan to ensure the catheters did not move and are still in the proper place
- Obtain pathology report and verify diagnosis

- Administration of study drug which will take approximately 6 hours (may last up to 12 hours)
- Study Drug Administration
 - Acquisition of study drug and diluent
 - Store syringes in refrigerator (4° C) until needed
 - Flush infusion tubing with diluent provided by pharmacy
 - Connect syringe with study drug to infusion tubing
 - Prime with 4.6 ml of the diluted virus preparation making sure that any excess study drug is disposed according to Biosafety Level 2 procedure
 - Connect tubing to catheter
 - Place each syringe in syringe pump
 - Repeat for each active catheter
 - Program pump(s) to flush saline solution at a rate of 0.4 ml per catheter for 35 minutes
 - Re-program pump(s) to deliver study drug as follows:
 - Four (4) active catheters – 0.1ml/hour
 - Three (3) active catheters – 0.13 ml/hour
 - Two (2) active catheters – 0.2 ml/hour
 - One (1) active catheter – 0.4ml/hour
 - Begin infusion
 - After the 3 hour study drug infusion is complete (study drug syringe will not be empty) and prior to disconnecting first infusion tubing from catheter, flush second infusion tubing with diluent supplied by pharmacy
 - Obtain second syringes from refrigerator
 - Connect syringe to infusion tubing and prime with 4.6 ml of the diluted virus preparation
 - Disconnect first tubing from catheter and connect second tubing
 - Place syringe in syringe pump
 - Repeat for each active catheter
 - Program pump(s) to deliver study drug at
 - Four (4) active catheters – 0.1ml/hour
 - Three (3) active catheters – 0.13 ml/hour
 - Two (2) active catheters – 0.2 ml/hour
 - One (1) active catheter – 0.4ml/hour

- Begin infusion **If there is any problems with the catheters during the infusion, the PI and/or Co-PI are to be notified as well as the Study Coordinator**
- Obtain vital signs (pulse, blood pressure, respiratory rate and temperature) according to the following schedule:
 - Before initiation of study drug
 - Every hour for 12 hours post initiation
 - Every 2 hours for the next 12 hours
 - Every 4 hours for the next 24 hours
- Perform a neurological (nervous system) examination to include assessment of cranial nerve abnormalities, gait abnormalities (when appropriate), sensory abnormalities, muscle strength, and level of consciousness:
 - Before initiation of study drug
 - Every hour for 12 hours post initiation
 - Every 2 hours for the next 12 hours
 - Every 4 hours for the next 24 hours
- AE monitoring
- After infusion is completed (study drug syringe will not be empty), the catheters will be disconnected from the infusion tubing and capped off. The catheters will remain in place for 6-18 hours and then removed.
- Should a patient have an access device (eg., Rickham or Ommaya reservoir) that accesses either the more central portion of the tumor/cyst, or the CSF space, fluid will be aspirated as possible (expected, 2-10cc) from the catheter for laboratory studies. These specimens will be obtained at either the pre op clinic visit or the day of surgery, as well as up to daily during the inpatient hospitalization (per the surgeon's discretion), and again at post op visit day 10, Day 28, and Months 3,6,9 and 12

Day 2:

- Continuation of vital signs and neurological examinations (see Day 1 for schedule)
- Wound examination
- Review of medications
- Collect blood for the following:
 - CBC with diff and platelets
 - Serum Chemistry (sodium, potassium, chloride, bicarbonate, glucose, BUN, creatinine, calcium, phosphorus, total protein, uric acid, GGT, AST/ALT, CK, LDH, alkaline phosphatase, total bilirubin, cholesterol, triglyceride)
 - PT/INR, PTT
 - HSV detection
 - IL-12 detection
 - LTA Elispot
 - IFN gamma assay
 - Immune studies - to be stored for future research
- Collect samples of conjunctival (eye) secretions and saliva for HSV detection
- AE monitoring
- Should a patient have an access device (eg., Rickham or Ommaya reservoir) that accesses either the more central portion of the tumor/cyst, or the CSF space, fluid will be aspirated as possible (expected, 2-10cc) from the catheter for laboratory studies. These specimens will be obtained at either the pre op clinic visit or the day of surgery, as well as up to daily during the inpatient hospitalization (per the surgeon's discretion), and again at post op visit day 10, Day 28, and Months 3,6,9 and 12

Day 3:

- Continuation of vital signs and neurological examinations (see Day 1 for schedule)
- Wound examination
- Review of medications
- Complete the Karnofsky Performance Scale (KPS)
- Obtain MRI scan prior to discharge

- Collect blood for the following:
 - HSV detection
 - IL-12 detection
 - LTA Elispot
 - IFN gamma assay
 - Immune studies - to be stored for future research
- AE monitoring
- Discharge if subject is stable enough to leave the hospital
- Should a patient have an access device (eg., Rickham or Ommaya reservoir) that accesses either the more central portion of the tumor/cyst, or the CSF space, fluid will be aspirated as possible (expected, 2-10cc) from the catheter for laboratory studies. These specimens will be obtained at either the pre op clinic visit or the day of surgery, as well as up to daily during the inpatient hospitalization (per the surgeon's discretion), and again at post op visit day 10, Day 28, and Months 3,6,9 and 12

Day 10 ± 3 days:

- Review medications
- AE monitoring
- Obtain vital signs (pulse, blood pressure, respiratory rate, temperature and weight)
- Perform a complete physical exam
- Wound examination
- Perform a neurological (nervous system) examination to include assessment of cranial nerve abnormalities, gait abnormalities (when appropriate), sensory abnormalities, muscle strength, and level of consciousness
- Complete the Karnofsky Performance Scale (KPS)
- Collect blood for the following:
 - CBC with diff and platelets
 - Serum Chemistry (sodium, potassium, chloride, bicarbonate, glucose, BUN, creatinine, calcium, phosphorus, total protein, uric acid, GGT, AST/ALT, CK, LDH, alkaline phosphatase, total bilirubin, cholesterol, triglyceride)
 - PT/INR, PTT
 - HSV antibody titer
 - HSV detection
 - IL-12 detection
 - LTA Elispot
 - IFN gamma assay
 - HSV detection
 - Immune studies - to be stored for future research
- Collect samples of conjunctival (eye) secretions and saliva for HSV detection
- Should a patient have an access device (eg., Rickham or Ommaya reservoir) that accesses either the more central portion of the tumor/cyst, or the CSF space, fluid will be aspirated as possible (expected, 2-10cc) from the catheter for laboratory studies. These specimens will be obtained at either the pre op clinic visit or the day of surgery, as well as up to daily during the inpatient hospitalization (per the surgeon's discretion), and again at post op visit day 10, Day 28, and Months 3,6,9 and 12

Day 28 ± 4 days:

- Review medications
- AE monitoring
- Obtain vital signs (pulse, blood pressure, respiratory rate, temperature and weight)
- Perform a complete physical exam
- Perform a neurological (nervous system) examination to include assessment of cranial nerve abnormalities, gait abnormalities (when appropriate), sensory abnormalities, muscle strength, and level of consciousness
- Complete the Karnofsky Performance Scale (KPS)

- Collect blood for the following:
 - CBC with diff and platelets
 - Serum Chemistry (sodium, potassium, chloride, bicarbonate, glucose, BUN, creatinine, calcium, phosphorus, total protein, uric acid, GGT, AST/ALT, CK, LDH, alkaline phosphatase, total bilirubin, cholesterol, triglyceride)
 - PT/INR, PTT
 - HSV antibody titer
 - HSV detection
 - IL-12 detection
 - LTA Elispot
 - IFN gamma assay
 - Immune studies - to be stored for future research
- Collect samples of conjunctival (eye) secretions and saliva for HSV detection
- Obtain MRI scan
- Discontinue prophylactic AED medication (if applicable)
- Should a patient have an access device (eg., Rickham or Ommaya reservoir) that accesses either the more central portion of the tumor/cyst, or the CSF space, fluid will be aspirated as possible (expected, 2-10cc) from the catheter for laboratory studies. These specimens will be obtained at either the pre op clinic visit or the day of surgery, as well as up to daily during the inpatient hospitalization (per the surgeon's discretion), and again at post op visit day 10, Day 28, and Months 3,6,9 and 12

Month 2 (study coordinator visit):

- Review medications
- AE monitoring
- Collect blood for the following:
 - CBC with diff and platelets
 - Serum Chemistry (sodium, potassium, chloride, bicarbonate, glucose, BUN, creatinine, calcium, phosphorus, total protein, uric acid, GGT, AST/ALT, CK, LDH, alkaline phosphatase, total bilirubin, cholesterol, triglyceride)
 - PT/INR, PTT
 - HSV detection
- Collect samples of conjunctival (eye) secretions and saliva for HSV detection

Month 3:

- Review medications
- AE monitoring
- Obtain vital signs (pulse, blood pressure, respiratory rate, temperature and weight)
- Perform a complete physical exam
- Perform a neurological (nervous system) examination to include assessment of cranial nerve abnormalities, gait abnormalities (when appropriate), sensory abnormalities, muscle strength, and level of consciousness
- Complete the Karnofsky Performance Scale (KPS)
- Collect blood for the following:
 - CBC with diff and platelets
 - Serum Chemistry (sodium, potassium, chloride, bicarbonate, glucose, BUN, creatinine, calcium, phosphorus, total protein, uric acid, GGT, AST/ALT, CK, LDH, alkaline phosphatase, total bilirubin, cholesterol, triglyceride)
 - PT/INR, PTT
 - HSV antibody titer
 - HSV detection
 - IL-12 detection
 - LTA Elispot
 - IFN gamma assay
 - Immune studies - to be stored for future research

